1.5. Randomization and Blinding

Randomization will be used to minimize bias in the assignment of participants to treatment groups, to increase the likelihood that known and unknown participant attributes (e.g., demographic and baseline characteristics) are evenly balanced across treatment groups, and to enhance the validity of statistical comparisons across treatment groups. Blinded treatment will be used to reduce potential bias during data collection and evaluation of clinical endpoints.

Intervention Allocation

Central randomization will be implemented in this study. Participants will be randomly assigned to 1 of 3 intervention groups (1:1:1 ratio), based on a computer-generated randomization schedule prepared before the study by or under the supervision of the sponsor. The randomization will be balanced by using randomly permuted blocks and will be stratified by corticosteroid use at baseline (yes, no). The interactive web response system (IWRS) will assign a unique treatment code, which will dictate the treatment assignment and matching study intervention kit(s) for the participant.

The requestor must use his or her own user identification and personal identification number when contacting the IWRS and will then be given the relevant participant details to uniquely identify the participant.

Blinding

To maintain the study blind, the study intervention container will have a label containing the study name, study intervention number, and reference number. The study intervention number will be entered in the electronic case report form (eCRF) when the study intervention is dispensed. Each active study intervention and its matching placebo will be identical in appearance.

Data that may potentially unblind the treatment assignment (e.g., study intervention serum concentrations, antibodies to study intervention) will be handled with special care to ensure that the integrity of the blind is maintained and the potential for bias is minimized. This can include making special provisions, such as segregating the data in question from view by the investigators, clinical team, or others as appropriate until the study unblinding.

The post-baseline results of CRP and fecal calprotectin tests performed by the central laboratory will be blinded to the study sites. If a study site requests these data, it will be provided to them after the analyses based on the Final Safety DBL have been completed.

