5.2. Analysis Specifications

5.2.1. Level of Significance

A 2-sided significance level of 0.2 (equivalent to the 1-sided 0.1 level specified in the protocol) will be used for all hypothesis testing and no adjustments for multiple comparisons will be made. Nominal p-values will be presented.

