The difference in proportion of participants achieving clinical response at Week 12 between combination therapy and each monotherapy.

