5.3.3. Analysis Methods for the Primary Estimand (Estimand 1)

5.3.3.1. Main Estimator (Analysis) for the Primary Estimand

The primary endpoint, defined in Section 5.3.1, will be analyzed based on the Primary Estimand (Section 5.3.2). After accounting for the ICEs for the primary estimand (Estimand 1), participants who are missing any or all of the Mayo subscores that comprise the primary endpoint at Week 12 will be considered not to be in clinical response at Week 12 (i.e. nonresponder imputation).

In the primary analysis, data from all participants in the FAS (Section 2.2.2) will be analyzed according to the randomized study intervention regardless of the study intervention they actually received. The treatment difference between combination therapy versus each monotherapy will be tested using a 2-sided CMH chi-square test stratified by corticosteroid use at baseline (yes, no) at the 0.2 significance level. The magnitude of the treatment difference will be estimated by the difference in the proportion of participants achieving clinical response at Week 12 between the combination therapy group and each monotherapy group with a 2-sided 80% confidence interval (CI) calculated based on Wald statistic.

The study will be considered positive if the combination therapy group is significantly different from both monotherapy groups at the 2-sided significance level of 0.2 for the primary endpoint.

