5.4.3. Analysis Methods for the Main Estimand (Estimand 4)

5.4.3.1. Main Estimator (Analysis) for the Main Estimand

The major secondary endpoint will be analyzed based on the Main Estimand (Section 5.4.2). After accounting for the ICEs for the main estimand, participants who have a missing clinical remission status at Week 12 will be considered not to be in clinical remission at Week 12 (i.e. nonresponder imputation).

In this analysis for the major secondary endpoint, data from all participants in the FAS will be analyzed according to the randomized study intervention regardless of the study intervention they actually received. The treatment difference between combination therapy versus each monotherapy will be tested using a CMH chi-square test stratified by corticosteroid use at baseline (yes, no). The magnitude of the treatment difference will be estimated by the difference in the proportion of participants achieving clinical remission at Week 12 between combination therapy and each monotherapy with a 2-sided 80% CI calculated based on Wald statistic.

The testing of the major secondary endpoints will occur at a 2-sided significance level of 0.2 regardless of the significance of the primary endpoint. No adjustment for multiple comparisons will be made and nominal p-values will be presented.

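### The treatment difference and its 80% Wald interval are described without the corticosteroid strata used in randomisation and in the CMH test: a free improvement with a small effect

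*SAP*

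**What the plan says.** SAP 1.5 and protocol 6.3 randomise in permuted blocks within two strata: corticosteroid use at baseline, yes or no. There is no other stratification factor.

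For the primary endpoint, SAP 5.3.3.1 tests each comparison with a "2-sided CMH chi-square test stratified by corticosteroid use at baseline (yes, no) at the 0.2 significance level". The following sentence estimates the effect as the difference in response proportions, with a 2-sided 80% "confidence interval (CI) calculated based on Wald statistic". It mentions no stratum, weighting or stratified standard error. SAP 5.4.3.1 repeats the pairing for clinical remission: a stratified CMH test, then a difference "with a 2-sided 80% CI calculated based on Wald statistic".

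The population-level summary in SAP 5.3.2 is: "The difference in proportion of participants achieving clinical response at Week 12 between combination therapy and each monotherapy". The success rule uses the tests alone: "The study will be considered positive if the combination therapy group is significantly different from both monotherapy groups at the 2-sided significance level of 0.2".

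Elsewhere the SAP does carry the factor into estimation. The subgroup logistic models (5.3.3.2, 5.4.3.2) and the ANCOVA and MMRM models (5.5.3) all include baseline corticosteroid use.

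**The concern.** Read plainly, the p-value conditions on the randomisation stratum while the estimate and interval beside it do not. When allocation is balanced within strata and the stratum predicts response, an unstratified standard error counts between-stratum variation that the design has already removed. The interval is then wider than needed, and it can include zero when the CMH test is significant, or the reverse.

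Protocol 2.1.2 says the study is meant to inform later combination studies. The difference and its interval are the size-of-effect result that such planning would use. The same pairing reaches further, because the Estimand 2 and Estimand 5 analyses and every tipping-point scenario refer back to 5.3.3.1.

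A response gap between strata is plausible. Steroid users must begin tapering at Week 6, and the medication rules in SAP Attachment 2 that turn a participant into a non-responder differ for users and non-users. The documents do not give the size of any gap.

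**Working it through.** **Inputs from the documents.** 70 per arm; response 75% (combination) and 55% (each monotherapy); 1-sided 0.1, which equals 2-sided 0.2, so z = 1.2816 for an 80% interval.

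**Assumptions not in the documents.** The share on steroids, w: 40% as base, 20% and 50% as range. The response gap between strata, g: 0 to 30 points, the same in both arms.

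**Step 1: the plan's own figure.** Simulating the two 1-sided chi-square tests with a shared combination arm gives 81.4% power at 55%/55%/75%, against the stated 81%. The six table rows come out at 79.2, 65.9, 69.1, 81.4, 89.8 and 85.4, against 79, 66, 69, 81, 90 and 85. The planning inputs are therefore read correctly.

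**Step 2: crude interval.** Half-width = 1.2816 × √[(0.75×0.25 + 0.55×0.45)/70] = 1.2816 × √(0.4350/70) = 10.10 points.

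**Step 3: stratified interval.** With balanced strata, the average within-stratum variance in an arm is p(1−p) − w(1−w)g². At w = 0.4 this removes 0.24g² per arm, or 0.48g² from the sum.

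| Assumed gap | Variance sum | Half-width (points) | Narrower than 10.10 |
|---|---|---|---|
| 0 | 0.4350 | 10.10 | none |
| 10 points | 0.4350 − 0.0048 = 0.4302 | 10.05 | 0.5% |
| 20 points | 0.4350 − 0.0192 = 0.4158 | 9.88 | 2.2% |
| 30 points | 0.4350 − 0.0432 = 0.3918 | 9.59 | 5.1% |

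For gaps of 10, 20 and 30 points, the half-widths are 10.07, 9.95 and 9.76 at 20% on steroids, and 10.04, 9.87 and 9.57 at 50%.

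**Step 4: coverage and agreement with the CMH test.** Simulation at 75% versus 55%, w = 0.4, strata balanced between arms, at least 200,000 trials per scenario. Disagreement means that the interval and the test differ about zero.

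| Gap | Crude: coverage | Crude: disagrees | Plain stratified Wald: coverage | Plain stratified Wald: disagrees |
|---|---|---|---|---|
| 0 | 79.3% | 0.2% | 78.9% | 0.5% |
| 10 | 79.6% | 0.3% | 78.8% | 0.6% |
| 20 | 80.5% | 0.7% | 78.6% | 0.7% |
| 30 | 81.7% | 1.6% | 78.8% | 0.4% |

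If the true difference is 10 points, the crude interval disagrees in about 2.5% of trials at a 30-point gap. If the strata are not balanced between arms, it disagrees in about 1% to 5% over gaps of 0 to 30 points.

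**Step 5: n−1 in the stratum variances.** A Mantel-Haenszel difference whose variance divides by n−1 within each arm and stratum covers about 79% to 80%. It disagrees with the CMH test in about 0.1% of trials at every gap in the table.

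This correction uses up a little of the gain in width. Because it makes the variance unbiased, the interval averages the Step 3 widths. The crude interval, which divides by n, averages about 10.10 × √(69/70) = 10.03. Against 10.03, the gain is nil at gaps of 0 and 10 points, (10.03 − 9.88)/10.03 = 1.5% at 20 points, and (10.03 − 9.59)/10.03 = 4.4% at 30 points.

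**The case against.** The case on the other side has four parts.

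- **The SAP never says crude.** A Wald interval can be built on a CMH-weighted difference. This stands: the unstratified reading is the natural one, but it is an inference. If a stratified interval was meant, the SAP leaves two programmers free to produce different primary intervals, and the same sentence cures that.
- **Too wide is not established.** A reader might infer that the planned interval is plainly too wide. The documents give neither the share on steroids nor response by stratum. With no gap there is nothing to gain, and up to 20 points the crude interval covers close to its nominal 80%. This stands. The supportable statement is that the interval can be slightly wider than needed.
- **A stratified Wald interval is not a clean remedy.** The plain version under-covers slightly at every gap, and at gaps of 0 and 10 points it disagrees with the CMH test more often than the crude one does. CMH uses a null variance, so neither matches it exactly. This stands against the plain formula. The n−1 version answers it, so the objection changes the variance formula and not the recommendation.
- **The simple difference already estimates the stated summary.** It does. Under 1:1 allocation, however, Mantel-Haenszel weights are essentially proportional to stratum size, and with exactly balanced strata the two point estimates coincide. Stratifying does not change the target.

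A reader might also infer that the mismatch threatens the trial's conclusion. It does not: success depends only on the two CMH tests, so type I error and power are as planned.

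**Conclusion.** The point holds as a small, free improvement. Randomisation, the primary and major secondary tests, and the SAP's other models all use the corticosteroid stratum; the main effect estimate and its interval, as worded, do not. At the planning rates and an assumed 40% on steroids, the saving is about 0.05, 0.2 and 0.5 points on a half-width of 10.1 for assumed gaps of 10, 20 and 30 points, and zero without a gap. With balanced strata, disagreement between crude interval and test stays below 2% at the planning difference.

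These sizes depend on the assumed share and gaps, on a constant treatment difference across strata, and on the response rates. They were worked for clinical response. The SAP gives no planning rate for clinical remission, so for 5.4.3.1 the finding concerns the wording, and its size is not quantified here.

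**What to change.** In SAP 5.3.3.1 and 5.4.3.1, state that the treatment difference is the Mantel-Haenszel stratum-weighted risk difference, using the same corticosteroid strata as the CMH test. State that its 2-sided 80% interval comes from a stratified variance with n−1 in place of n within each arm and stratum. The analyses that refer back to 5.3.3.1 then inherit the definition.

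The cost is one sentence in each section and a small amount of programming. If the software's stratified option uses the plain variance, the n−1 version needs a few extra lines. No new data are needed, and the tests and success rule stay as they are. The SAP treats the Week 12 database lock as still to come, so the wording can be settled before it. Because some sponsor staff have seen interim data, the change should be dated and its reason recorded.

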5.3.3.2. Subgroup Analyses

Subgroup analyses will be performed (if the number of participants within each subgroup level permits) based on demographic and baseline disease characteristics, baseline concomitant UC medication use, and history of UC-related medications specified in Section 2.3. Note that, for subgroup analyses, the analysis sets are the individual subgroups of the FAS. A forest plot will be produced for all subgroups. Odds ratio of the combination therapy group versus each monotherapy group and the associated 80% CI from a logistic regression model will be provided for each of subgroups. The logistic regression model will include treatment group and corticosteroid use at baseline (yes, no) as the factors. For subgroup analyses of corticosteroid use at baseline (yes, no), treatment group will be the only the factor in the model. The primary estimand (Estimand 1) will be used for these subgroup analyses.

5.3.3.3. Sensitivity Analyses

For the primary estimand (Estimand 1), after accounting for the ICEs, the proportion of participants with missing clinical response status at Week 12 is expected to be quite small. Despite the expectation of a very small percentage of missing data at Week 12, the following sensitivity analysis will be performed using a tipping point analysis with exhaustive scenarios.

The following method will be utilized to vary the imputation of clinical response status at Week 12 for missing data after the intercurrent event rules have been applied. For participants with missing data at Week 12, the clinical response status will be imputed in an increasing manner by participant level for each study intervention. Specifically, for each participant, a responder/non-responder status will be imputed starting with the scenario where all participants are non-responders up to the scenario where all participants are responders. This would include all possible

scenarios of responder status for all missing data. For each scenario, an analysis same as described above in Section 5.3.3.1 for the primary analysis for the primary estimand will be performed.

5.3.4. Supplementary Estimands

Two supplementary estimands (Estimands 2 and 3) are considered to support the primary estimand for the primary endpoint (Estimand 1).

5.3.4.1. Estimand 2

In this supplementary estimand for the primary endpoint (Estimand 2), all ICEs (Section 5.3.2) will be addressed by the **composite strategy**.

The attributes of this supplementary estimand are the same as those for the primary estimand (Estimand 1) with the exception of the Variable (Endpoint) and strategy for ICEs, which is described as follows:

Variable (Endpoint): Clinical response at Week 12. Participants who have any ICE in categories 1-5 (listed in Section 5.3.2) prior to the Week 12 visit will be considered not to have achieved clinical response at Week 12, regardless of the observed data.

5.3.4.2. Estimand 3

In this supplementary estimand for the primary endpoint (Estimand 3), all ICEs (Section 5.3.2) will be addressed by the **hypothetical strategy**.

The attributes of this supplementary estimand are the same as those for the primary estimand (Estimand 1) with the exception of the Variable (Endpoint) and strategy for ICEs, which is described as follows:

Variable (Endpoint): Clinical response at Week 12. Participants who have any ICE in categories 1-5 (listed in Section 5.3.2) prior to the Week 12 visit will be considered to have **missing** clinical response status at Week 12, regardless of the observed data.

This supplementary estimand uses a **hypothetical strategy** that considers the clinical response status at Week 12 after the ICE to be the same as for other participants in the same study intervention who had not yet experienced the ICE. The **hypothetical strategy** attempts to estimate the treatment effect if the randomized treatment is taken as specified in the protocol. As such, any clinical response status observed after an ICE is excluded in order to ensure results reflect participant experience on randomized treatment only. Therefore, utilizing the hypothetical estimand allows for an analysis of participants under the scenario when they are compliant with the investigative therapy, and thus, is justified clinically since it attempts to eliminate the potentially confounding effects due to ICEs.

5.3.5. Estimators (Analyses) for the Supplementary Estimands

5.3.5.1. Estimator (Analysis) for Estimand 2

For the supplementary analysis of the primary endpoint based on Estimand 2, after accounting for the ICEs for this supplementary estimand, participants who have a missing clinical response status at Week 12 will be considered not to be in clinical response at Week 12 (i.e. nonresponder imputation).

In this supplementary analysis, data from all participants in the FAS (Section 2.2.2) will be analyzed according to the randomized study intervention regardless of the study intervention they actually received. The analysis method is same as that for the main estimator (analysis) for the primary estimand (Estimand 1). Refer to Section 5.3.3.1 for details.

5.3.5.2. Estimator (Analysis) for Estimand 3

For the supplementary analysis of the primary endpoint based on Estimand 3, after accounting for the ICEs for this supplementary estimand, the missing status of clinical response at Week 12 will be imputed using multiple imputation (MI) as described in Table 3, under the assumption that the data are missing at random (MAR) for all participants in the FAS. The MI will be performed on each Mayo subscore with missing data and then the clinical response status at Week 12 will be derived from such imputed Mayo subscores.

Table 3: Multiple Imputation Methods		
Endpoints	MI specification	Analysis method/Summary statistics
Clinical Response at Week 12	Multiple imputation with full conditional specification (FCS) regression of subscores	MIMayoData1 (N=200, Seed=4362478) 
 Imputation variables: 4 Mayo subscores from Week 0 – 12 (after accounting for ICEs) Ancillary variables: Treatment group, corticosteroid use at baseline (yes, no)

In this supplementary analysis, data from all participants in the FAS will be analyzed according to the randomized study intervention regardless of the study intervention they actually received. For each of the N imputation datasets, the treatment difference between combination therapy versus each monotherapy will be tested using a 2-sided CMH chi-square test stratified by corticosteroid use at baseline (yes, no). The analysis results from all the imputation datasets will be combined according to Rubin¹⁰, and the p-value for testing the treatment difference will be obtained.

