1.4. Sample Size Justification

A sample size of 210 participants (70 per intervention group) was determined by the power to detect a significant difference in the proportion of participants in clinical response at Week 12 (primary endpoint) between the combination therapy and both monotherapies using a 1-sided chi-square test with 0.1 significance level for each comparison. The study is sized such that the

combination therapy has approximately 80% power (based on simulations) to achieve both comparisons to monotherapy for the primary endpoint.

The assumptions for the sample size calculations were based on data from the past golimumab programs conducted by the sponsor in participants with UC who were naïve to biologic therapy. The proportion of participants in clinical response at Week 12 is expected to be 55% for golimumab compared to 51% observed at Week 6 in study C0524T17 (PURSUIT), as the PURSUIT program suggested that the response rate might increase slightly with further treatment. This was also confirmed in study CNTO148UCO2001 (PROgECT)¹³. The tested dose of guselkumab is assumed to have the same clinical response rate as golimumab at Week 12. The proportion of participants in clinical response at Week 12 is assumed to be 75% for the combination therapy, which is based on the additive effect from both monotherapies (20% improvement from each monotherapy relative to a historical placebo response of 35%). The different combinations of clinical response rate assumptions and associated power are displayed in [Table 1](#).

Golimumab (n=70)	Guselkumab (n=70)	Combination Therapy (n=70)	Power
50%	50%	70%	79%
50%	55%	70%	66%
55%	60%	75%	69%
55%	55%	75%	81%
55%	60%	80%	90%
60%	60%	80%	85%

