5.4.1. Definition

Clinical remission: the Mayo score ≤ 2 with no individual subscore >1 .

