5.4.5. Estimators (Analyses) for the Supplementary Estimands

5.4.5.1. Estimator (Analysis) for Estimand 5

For the supplementary analysis of the major secondary endpoint based on Estimand 5, after accounting for the ICEs for this supplementary estimand, participants who have a missing clinical remission status at Week 12 will be considered not to be in clinical remission at Week 12 (i.e. nonresponder imputation).

In this supplementary analysis for the major secondary endpoint, data from all participants in the FAS (Section 2.2.2) will be analyzed according to the randomized study intervention regardless of the study intervention they actually received. The analysis method is same as that for the main estimator (analysis) for the primary estimand (Estimand 1). Refer to Section 5.3.3.1 for details.

5.4.5.2. Estimator (Analysis) for Estimand 6

For the supplementary analysis of the major secondary endpoint based on Estimand 6, after accounting for the ICEs for this supplementary estimand, the missing status of clinical remission at Week 12 will be imputed using MI. For participants with missing status of clinical remission at Week 12, their clinical remission status at Week 12 will be derived from the imputed Mayo subscores in MIMayoData1 that has been created in Section 5.3.5.2.

The analysis method based on this supplementary estimand (Estimand 6) for the major secondary endpoint is same as the analysis method based on the supplementary estimand (Estimand 3) for the primary endpoint. Refer to Section 5.3.5.2 for details.

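### Supplementary Estimands 3 and 6 leave the imputation scale and the pooled quantity undefined and report no effect estimate; unrounded linear draws would understate remission among imputed participants by roughly 40–67%

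*SAP*

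**What the plan says.** SAP 5.3.4.2 defines Estimand 3. Every participant with an intercurrent event of any of the five categories before Week 12 is treated as missing. All other attributes of Estimand 1 are kept, including its population-level summary, the difference in response proportions (SAP 5.3.2).

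SAP 5.3.5.2 and Table 3 give the estimator. The model is "Multiple imputation with full conditional specification (FCS) regression of subscores", with 200 data sets and a fixed seed, using the four Mayo subscores over Weeks 0–12, treatment group and baseline corticosteroid use. Each missing subscore is imputed and response status is derived from the result. A stratified CMH chi-square test is run in each data set. Then: "The analysis results from all the imputation datasets will be combined according to Rubin". The only output named is a p-value.

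Estimand 6 (SAP 5.4.5.2) reuses these data sets. For participants without a Week 12 status, "their clinical remission status at Week 12 will be derived from the imputed Mayo subscores in MIMayoData1", and the analysis follows Estimand 3. SAP 5.4.1 defines remission as a Mayo score of at most 2, "with no individual subscore" above 1. SAP 5.3.1 requires, for response, a rectal bleeding subscore that falls by at least 1 or equals 0 or 1, alongside the drop in total score.

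**The concern.** There are two separate gaps.

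**Imputation scale.** Subscores are integers from 0 to 3 (SAP 5.3.1.1). A linear regression draw is continuous and can be 1.3 or −0.4. A draw centred on 1 exceeds 1 about half the time and then fails the remission rule. Read literally, the response branch that needs a bleeding subscore of 0 or 1 almost never holds for a continuous draw. Two programmers following Table 3 could therefore derive materially different rates.

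**Pooling and output.** Rubin's rules combine an estimate and its variance. A CMH chi-square on one degree of freedom has no direction and no variance, and the SAP does not say how it is put on a usable scale. Estimands 1, 2, 4 and 5 each get a difference with an 80% CI; Estimands 3 and 6 do not. The hypothetical-strategy effect then cannot be set beside the main effect, which is what a supplementary estimand is for.

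**Working it through.** **The plan's own figure.** The documents give no imputed remission rate to reproduce. The nearest stated figure is the power in SAP 1.4: "combination therapy has approximately 80% power (based on simulations" to win both comparisons, "using a 1-sided chi-square test with 0.1 significance level for each comparison", with 70 per arm. With pooled-variance z tests, z = (p₁ − p₂)/√(2p̄(1 − p̄)/70), critical value 1.2816 and a shared combination arm, the rates 55/55/75% give 0.89 for one comparison and 0.814 for both, against 81% in SAP Table 1. The other five rows also reproduce. These response rates anchor the simulation below.

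**Inputs assumed, because the documents give none.**
- Missing share at Week 12: 5%, 10% and 20%.
- Subscore correlations: two settings of correlated latent normals cut to 0–3.
- Remission rates: about 9–14% on monotherapy and 20–26% on combination in the runs near 55/55/75% response. Protocol 2.1 cites only rates below 20% for biologic monotherapies.

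**Imputed remission.** Bayesian linear-regression FCS with the Table 3 variables, 70 per arm, baseline Mayo at least 6 and endoscopy at least 2. The imputed status is compared with the true status of the same missing participants. Six of the twelve scenarios:

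| Correlation setting | Missing | True | Unrounded | Rounded | Predictive mean matching | Shift in whole-FAS rate, unrounded |
|---|---|---|---|---|---|---|
| Higher | 5% | 17.4% | 6.0% | 12.7% | 15.7% | −0.6 points |
| Higher | 10% | 17.7% | 7.4% | 14.4% | 16.4% | −1.0 |
| Higher | 20% | 18.1% | 7.6% | 14.4% | 15.4% | −2.1 |
| Lower | 5% | 12.8% | 5.6% | 12.6% | 14.0% | −0.4 |
| Lower | 10% | 15.2% | 6.5% | 13.7% | 13.5% | −0.9 |
| Lower | 20% | 14.8% | 6.4% | 13.1% | 14.6% | −1.7 |

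The last column is missing share × (imputed − true). For example, 0.20 × (7.6 − 18.1) = −2.1 points.

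Ratios of imputed to true rate over all twelve scenarios:
- Remission, unrounded: 0.33–0.44. In further scenarios with true remission of 34–66% it was 0.51–0.60. The loss is therefore 1 − 0.60 = 40% to 1 − 0.33 = 67%.
- Remission, rounded: 0.71–0.99; rounded and clipped to 0–3: 0.69–0.92.
- Remission, predictive mean matching: 0.77–1.10, closer to the truth than rounding in 10 of the 12.
- Response, unrounded: 0.74–0.83, a loss of 17–26%; rounded: 0.90–0.99, a loss of 1–10%.

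I have no Monte Carlo standard errors for these ratios, so the second decimal should not be relied on.

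**Pooling.** Rubin's total variance is T = Ū + (1 + 1/M)B, where Ū is the mean within-imputation variance and B the between-imputation variance. Simulated type I error at nominal two-sided 0.2:

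| Missing | Average of raw chi-squares | Wilson–Hilferty transform, then Rubin | Risk difference pooled by Rubin |
|---|---|---|---|
| 5% | 0.217 | 0.201 | 0.202 |
| 10% | 0.235 | 0.200 | 0.201 |
| 20% | 0.291 | 0.195 | 0.198 |

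**The case against.** A reader might infer that the plan halves the remission rate. The documents do not support that. Table 3 says neither that the regression is linear nor that draws stay unrounded, and the large loss needs both. Even then it applies only to imputed participants.

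A reader might also infer that pooling through CMH tests lowers the rate, or that the pooling is invalid. Pooling cannot change an imputed rate. A Wilson–Hilferty transform gives a valid pooled p-value, and the SAP does not prescribe averaging raw statistics. The method is under-specified, not shown to be wrong.

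The SAP expects few missing values (5.3.3.3), but says so for Estimand 1. Estimands 3 and 6 also set all participants with intercurrent events to missing, so more is imputed; how much is unknown.

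The Table 3 column headed for analysis method and summary statistics holds only imputation settings in the text available, so cells may have shifted. The paragraph after the table still names only a p-value.

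The scope objection stands. Study success rests on Estimand 1 with nonresponder imputation and a tipping-point analysis, the main remission analysis also uses nonresponder imputation, and Estimands 3 and 6 decide nothing. It also stands that the Table 3 method serves the ANCOVA of Mayo change (SAP 5.5.3), where no threshold applies and unrounded draws raise no such problem.

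**Conclusion.** The concern holds as an under-specification with a material consequence under one plain reading. How far the imputed remission and response rates fall depends on a rounding choice that the SAP leaves open. The ranges in the working rest on assumed correlations, missing shares and remission rates. In the whole Full Analysis Set the unrounded remission effect is modest, about 1–2 points at 10–20% missing. The absence of a pooled difference and CI rests on no simulation: it follows from comparing SAP 5.3.5.2 with the summary in 5.3.2. The correction is worth making because the text as it stands does not estimate its own estimand, but no primary or main secondary conclusion depends on it.

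**What to change.** In Table 3, for the binary endpoints derived from MIMayoData1, specify FCS predictive mean matching, or ordinal logistic regression if it converges, so that imputed subscores are integers from 0 to 3. State whether the same data sets serve the ANCOVA of Mayo and modified Mayo change in SAP 5.5.3.

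In SAP 5.3.5.2, and through it 5.4.5.2, estimate in each data set the Mantel–Haenszel risk difference stratified by baseline corticosteroid use, with its standard error. Pool these by Rubin's rules and report the difference, 80% CI and p-value for each comparison.

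The cost is SAP wording and minor programming, with no new data. The ordinal model may fail to converge with sparse categories. Predictive mean matching avoids that, though the simulation does not show exact recovery of the true rate.
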